#### *Primary outcome:*

Based on the adult and the limited pediatric data available we hypothesize that propofol infusion in sub anesthetic dose, will result in either complete resolution or improve the headache pain scores by 50% from the baseline pain scores. Patients will be assessed with a 0-10 Numeric Pain Rating Scale.

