#### *Secondary outcomes:*

- Time to beginning of effect (from the beginning of the propofol infusion till first improvement in pain score noted)
- Duration of effect (from the end of propofol administration till discharge criteria are meet or if treatment is ineffective, till start of new therapy)
- Total propofol dose based on weight.

Goal of subjects to be consented include: 30 to demonstrate effect

Subjects may receive multiple treatments if propofol infusion is effective in reducing headache symptoms.

**Concise Summary:** We will be enrolling subjects who are scheduled to undergo DHE infusion for treatment of migraine headaches as part of standard medical care. Subjects will be identified from the investigators' patient list, of children presenting to the Headache Clinic in the Pain Management Clinic for treatment of migraine headache or who have been admitted to the hospital for treatment of migraine headache. Patients who will be treated at the SPU or during inpatient admission by the DHE protocol will be evaluated for eligibility prior to the visit. If the investigator determines that they would be

eligible, the family will be contacted in advance of the visit to discuss possible participation. An investigator will be present at the visit to discuss the study in further detail and answer any questions, and informed consent will be obtained prior to any study procedures are performed.

Prior to initiation of DHE infusion, the subjects will receive sub-anesthetic doses of propofol infusion: 20 mcg/kg/min for 10 minutes, followed by an increase to 30 mcg/kg/min for 10 minutes and then by an increase to 40 mcg/kg/min for 40 minutes. The propofol infusion will be terminated if:

- The patient has no pain, or greater than 50% reduction in pain scores as compared to the pretreatment pain score
- After completing 40 minutes of propofol infusion at 40 mcg/kg/min irrespective of the pain score
- If the anesthesiologist feels cardio-pulmonary depression, airway obstruction or over sedation (Ramsay Sedation Score greater than 3) has occurred

If the propofol infusion is effective in resolving headache symptoms, then subjects will be monitored for at least 30 minutes after termination of infusion. Outpatient subjects would then be discharged home; inpatient subjects would resume standard care treatment.

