### **B. Protocol**

Patients will be recruited from the investigators patients in the headache clinic or from inpatient consults to the pain service.

Patients may be identified once scheduled for DHE infusion at the CMC Special Procedures Unit (SPU) for treatment of migraine headaches, or once the pain team is consulted for inpatient subjects who have been admitted for migraine symptoms.

Upon identification of potential subjects, if the patients meet inclusion criteria, a study investigator will describe the study details as well as the alternative DHE therapy. Should the patient's guardian consent and the patient assent we will continue with the study protocol. **If consent will be obtained the study will proceed as follows:**

- A urine pregnancy test will be performed for all female of child-bearing potential as standard care in accordance with CMC policy. The patient will have an IV catheter placed as part of standard of care treatment for DHE infusion. A peripheral vein will be accessed and an infusion of Ringer lactate will be started. For the intravenous access, a topical anesthetic (i.e. j-tip or synera patch) will be used as per SPU protocol.
- Patients will be continuously monitored as per ASA guidelines to include continuous pulse-oximetry, EKG, respiratory monitoring and heart rate. The attending anesthesiologist (investigator) will be physically present at the start of study drug infusion; he will also be immediately available in the SPU or main hospital for the duration of the infusion period.

- pain scores (Numeric Pain Rating Scale) will be evaluated during study medication titration, before, every 10 minutes throughout infusion and up to one hour after termination of the infusion.
- sedation scores will be evaluated by using the Ramsay Sedation Scale before, every 10 minutes throughout infusion and up to one hour after termination of the infusion.
- The propofol will be delivered through an infusion pump (Alaris) starting at a rate of 20 mcg/kg/min for 10 minutes, followed by an increase to 30 mcg/kg/min for 10 minutes and then by an increase to 40 mcg/kg/min for 40 minutes
- The propofol infusion will be terminated if:
  - The patient has no pain, or greater than 50% reduction in pain scores as compared to the pretreatment pain score
  - After completing 40 minutes of propofol infusion at 40 mcg/kg/min irrespective of the pain score

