### 3. Study termination

- if patient has no pain or greater than 50% reduction in pain scores as compared to the pretreatment pain score, then outpatient subjects will be monitored in the SPU for 1 hour. If no clinically significant side effects are present after one hour, then the IV will be removed and he will be discharged with appropriate instructions from primary headache provider for home care and follow-up. Discharge criteria will follow CMC Perianesthesia Department policy for discharge, Policy Number 1.06. Inpatient subjects who have no pain will resume standard care treatment and will be discharged at the discretion of the attending service.
- if patient has less than 50% reduction in pain scores, the study investigators will continue with DHE protocol according to standard of care.

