Title: Low- Dose Propofol Infusion as an Abortive Treatment for Migraine Headaches in Pediatric Patients

NCT number: NCT02485418

Document date: December 29,2023

INTRODUCTION

The purpose of this statistical analysis plan (SAP) is to describe the procedures and the statistical methods that will be used to analyze and report results for study STU 042014-002 Low- Dose Propofol Infusion as an Abortive Treatment for Migraine Headaches in Pediatric Patients.

STUDY OVERVIEW

The aim of this prospective study was to evaluate the efficacy and safety of propofol administration in a hospital setting, as an abortive medication for children aged 7-18 with migraines.

We enrolled subjects who were scheduled to undergo DHE infusion for treatment of migraine headaches as part of standard medical care. Subjects were identified from the investigators' patient list, of children presenting to the Headache Clinic in the Pain Management Clinic for treatment of migraine headache or who had been admitted to the hospital for treatment of migraine headache. If the investigator determined that they were eligible, the family was contacted in advance of the visit to discuss possible participation. An investigator was present at the visit to discuss the study in further detail and answer any questions, and informed consent was obtained prior to any study procedures performed.

Prior to initiation of DHE infusion, the subjects received sub-anesthetic doses of propofol infusion:

20 mcg/kg/min for 10 minutes, followed by an increase to 30 mcg/kg/min for 10 minutes and then by an increase to 40 mcg/kg/min for 40 minutes.

If the propofol infusion was effective in resolving headache symptoms, then subjects were monitored for at least 30 minutes after termination of infusion. Outpatient subjects were discharged home.

If propofol infusion was not successful in resolving the headache, then the subjects proceeded with standard of care.

For all subjects who received a propofol infusion, follow-up occurred at 24 and 48 hours via phone call to evaluate headache status and recover information on headache symptoms and side effects.

STUDY OBJECTIVES

Primary Objective

Based on the adult and the limited pediatric data available we hypothesized that propofol infusion in sub anesthetic dose, would result in either complete resolution or improvement in headache pain scores by 50% from the baseline pain scores. Patients were assessed with a 0-10 Numeric Pain Rating Scale.

Secondary Objectives

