- Duration of effect (from the end of propofol administration till discharge criteria are meet or if treatment is ineffective, till start of new therapy)
- Total propofol dose based on weight.

Study Endpoints

The propofol infusion was terminated if:

- The patient had no pain, or greater than 50% reduction in pain scores as compared to the pretreatment pain score.
- After completing 40 minutes of propofol infusion at 40 mcg/kg/min irrespective of the pain score
- If the anesthesiologist feels cardio-pulmonary depression, airway obstruction or over sedation (Ramsay Sedation Score greater than 3) had occurred.

STATISTICAL ANALYSIS

Demographic and clinical characteristics for the sample of pediatric patients who received low- dose propofol infusion as an abortive treatment for migraine headaches were described using the sample mean and standard deviation for continuous variables and the frequency and percentage for categorical variables. The mean level of headache pain score at baseline and post-treatment (10-60 minute periods and 24- and 48-hour follow-up) was compared using the dependent samples t-test. Dependent samples t-test was also used to test for differences in the mean percent change in pain severity from baseline to each post-treatment assessment period. Statistical analyses were carried out using SAS software, version 9.4 (SAS Institute, Inc., Cary, NC). The level of significance was set at $\alpha=0.05$ (two-tailed).6.2. Data Analysis General Considerations

Sample Size Considerations

Forty patients were screened, and 38 patients participated in the study.

Handling of Missing Data

Missing data will not be imputed unless otherwise specified elsewhere in this SAP.

Protocol Deviations

Important protocol deviation criteria will be established, and subjects with important protocol deviations will be identified and documented.

Important protocol deviations will be summarized and listed by category for all subjects.

Safety Analyses

All safety analyses will be performed based on the Safety Analysis Set. Descriptive statistics will be used to analyze all safety data.

Adverse Events

Adverse events will be reported during scheduled follow-up communications and documented.

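### The hypothesis is complete relief or a 50% improvement, but the SAP tests only mean changes, so a significant result would not show that 50% was reached

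*SAP*

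**What the plan says.** The protocol's primary outcome is the hypothesis that the infusion "will result in either complete resolution or improve the headache pain scores by 50% from the baseline pain scores". The SAP's primary objective repeats it: "would result in either complete resolution or improvement in headache pain scores by 50% from the baseline pain scores". Neither says what share of children should reach that level, or when.

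The Statistical Analysis section of the SAP compares mean pain score at baseline with the mean at each later assessment (10 to 60 minutes, 24 hours, 48 hours) by dependent-samples t-test, and adds: "Dependent samples t-test was also used to test for differences in the mean percent change in pain severity from baseline". Significance is two-sided at 0.05. Frequencies and percentages are planned for demographic and clinical characteristics; response is not named among them.

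A criterion for the individual child does exist, as a rule for ending the infusion. The SAP lists it under Study Endpoints: "The patient had no pain, or greater than 50% reduction in pain scores as compared to the pretreatment pain score". The protocol's Study termination section uses the same threshold to decide care. It monitors outpatients for discharge "if patient has no pain or greater than 50% reduction in pain scores as compared to the pretreatment pain score, then outpatient subjects", and otherwise says "if patient has less than 50% reduction in pain scores, the study investigators will continue with DHE protocol according to standard of care".

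**The concern.** The hypothesis names a size of effect, and the planned tests do not refer to it. As written, they compare later scores with baseline, so the null value is no change. Rejecting that null says that mean pain fell. It does not say that pain fell by half, on average or in any given number of children.

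The wording also suggests sorting children one by one: pain-free, or improved by half. The background section reports the earlier propofol studies largely as rates (95.4% success and 82% complete resolution in adults, 80% efficacy in children). A mean change cannot be set beside those rates. The risk is that a small p-value is reported as support for the primary hypothesis when the analysis has not addressed it.

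**Working it through.** **Inputs from the documents.** Children: 38 (SAP, Sample Size Considerations). Two-sided alpha: 0.05 (SAP). Baseline pain: 6 to 10 on the 0-10 scale (protocol, Inclusion Criteria). The protocol's target of 30 cannot be reproduced, because no effect size, SD, response rate or power is given. The 38 is an enrolment count.

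**Assumed input.** SD of change in pain score: 1.5 to 3.5 points.

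**1. Smallest mean fall that is significant.** A paired t-test against zero is significant when mean fall > t(0.975, n−1) × SD / √n.
- t(0.975, 37) = 2.026 and √38 = 6.164, so the threshold is 2.026 / 6.164 = 0.329 SD.
- SD 1.5: 0.329 × 1.5 = 0.49 points, which is 4.9% of a baseline of 10 and 8.2% of a baseline of 6.
- SD 3.5: 0.329 × 3.5 = 1.15 points, which is 11.5% of 10 and 19.2% of 6.

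The threshold thus lies at roughly 5% to 19% of baseline, well below 50%.

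**2. A constructed case with no responders.** Take 38 children with baselines of 6 to 9; 19 fall by 1 point and 19 by 2.
- Mean fall 1.5 points, SD 0.507, t = 1.5 / (0.507 / 6.164) = 18.2, p about 4 × 10⁻²⁰.
- Mean reduction is 20%. The largest in any child is 2/6 = 33%, so none reaches 50%.

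**3. Does the mean percent change, read beside 50%, settle it?** Let every baseline be 8 (illustration).
- Case A: 8 children fall by 8 and 30 fall by 3. Mean fall (64 + 90)/38 = 4.05 points = 50.7%. Responders at 50% or more: 8/38 = 21% (Wilson 95% CI 11% to 36%).
- Case B: 36 children fall by 4 and 2 fall by 5. Mean fall (144 + 10)/38 = 4.05 points = 50.7%. Responders at 50% or more: 38/38; at more than 50%: 2/38.
- Against zero, both give p < 0.001. Against 50%, A gives p = 0.88 (95% CI 42% to 59%) and B gives p = 0.16 (49.7% to 51.6%).

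The same mean fits very different response rates. An interval set beside 50% would stop either case from being called a mean improvement above 50%, so that interval is worth having. It still does not give the number of responders.

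**4. Which score to use.** The protocol schedules the scores: "pain scores (Numeric Pain Rating Scale) will be evaluated during study medication titration, before, every 10 minutes throughout infusion and up to one hour" after the infusion. A full infusion of 10 + 10 + 40 = 60 minutes has six scores, and it stops at the first that shows more than 50% relief. A child whose pain varies around a higher level can be stopped on a chance low score, so the end-of-infusion rate alone may flatter the treatment. The documents give no score-to-score variation from which to size this.

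**5. Precision of a proportion.** 19/38 = 50%, Wilson 95% CI 35% to 65% (exact Clopper-Pearson: 33% to 67%).

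**The case against.** The strongest reply is that the hypothesis speaks of improving pain scores by 50%, which can mean an average improvement. On that reading the mean percent change is the right quantity, and what is missing is an interval and a comparison with 50%. This stands as a legitimate reading, and the fix provides for it. It does not rescue the plan as written, because the SAP states no 50% null value.

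A second reply is that a responder proportion would not show that the hypothesis was met either, since no benchmark rate is given. That is correct. The gain is an estimate of the quantity the hypothesis names. Setting a benchmark now, after enrolment is complete, would be worse than having none.

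A reader might also infer that the plan has no definition of response and no assessment times. The documents do not support that. The SAP lists the times and lacks only a designated main one. The stopping rule supplies a threshold for each child, and the Study termination section gives ineffective treatment, which matters for duration of effect, a working meaning: less than 50% reduction leads to DHE. A reduction of exactly 50% falls in neither branch of that section, but this is a narrow gap and how often it arose is not known.

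Nor should the constructed cases be read as evidence that few children responded. They use artificial patterns, in two of them a common baseline, and the documents contain no results.

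**Conclusion.** The concern holds: the planned efficacy tests can succeed without bearing on the 50% criterion in the primary hypothesis. At 38 children the threshold for significance is 0.33 SD, which needs no assumption about the SD but takes all 38 to have both scores. Its translation to about 0.5 to 1.2 points rests on the assumed SD of 1.5 to 3.5.

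This is a gap between hypothesis and analysis. It is not a claim that the t-tests are invalid or that the treatment failed. It is worth correcting because this is a completed single-arm study whose scheduled pain scores can answer the stated question descriptively. Nothing can be prespecified now: the SAP is dated December 2023 and already reports final enrolment.

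**What to change.** In the SAP, add one table and label it post hoc and descriptive:
- **Main result.** Number and proportion of children who are pain-free, and who are at least 50% improved, each with a 95% CI, at the end of infusion, with the number missing. Use the first infusion only, because the protocol says "Subjects may receive multiple treatments if propofol infusion is effective in reducing headache symptoms".
- **Threshold sensitivity.** Repeat with more than 50%, to match the stopping rule.
- **Second time.** Repeat at the last score within one hour after infusion and before any DHE, because the infusion stops at the first favourable score. Note that non-responders who go on to DHE may have a shorter window than responders.
- **Average reading.** Report the mean percent change with its 95% CI set beside 50%. Keep the t-tests as supporting results.
- **Limit.** State that no benchmark rate was set, so the table estimates response and does not formally test the hypothesis.

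The pain scores are already scheduled. DHE receipt is not a listed data item, and chart review is described only for eligibility and demographics, so the second time may need an extra chart check. The other costs are an imprecise proportion (19/38 would carry an interval of 35% to 65%) and a headline that may look less favourable than a small p-value.

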**Background:**

Headaches make up one of the largest somatic complaints in children and adolescents. Approximately 82% of adolescents report headaches before the age of 15. (8) Migraine headaches prevalence increases as children age. The reported prevalence increases from 3% (age 3 to 7 years) to 4 - 11% (age 7 to 11) and to 8 - 23% (age 11 to 15+). Mean age of onset differs from male to female, 7.2 years versus 10.9 respectively. (2) Migraine headaches, in particular, have significant impact on children. Repeated exacerbations lead to high levels of school absences, decreased participation in extracurricular activities and have been associated with several comorbid conditions. (9)

Migraine headache pathophysiology continues to be researched. There are many models available for discussion involving the presence of spreading cortical depression and regional blood flow changes. There is clear involvement of messenger molecules nitric oxide (NO) and calcitonin-gene-related peptide (CGRP). This involvement in the sensitization of perivascular nerve terminals and the origination of attacks from a central nervous system location continue to garner increasing attention. (10)

Per the American Academy of Neurology (AAN), treatment of migraine headaches in children has remained difficult. There is a lack of controlled data regarding the treatment of primary headache disorders in pediatrics. Acute treatment recommendations are extrapolated from pooled data of many studies. The recommendations from the AAN include the use of non-steroidal anti-inflammatories, ibuprofen in particular, acetaminophen, and sumatriptan. (2)

Acute medical system treatments of acute migraine exacerbations have been wide-spread as well. As currently the standard of care in acute migraine management is ill-defined. Most centers are

Protocol version dated 06Jan2017

proceeding with a combination therapy including: NSAIDs (typically ketorolac), acetaminophen, anti-nausea medications (metoclopramide, diphenhydramine, prochlorperazine). Should this therapy fail, these institutions proceed to hospital admission for further therapy including dihydroergotamine (DHE) and/or triptan therapy.

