## **13. Potential Benefits:**

1. Improved migraine abortive therapy with decreased side-effect profile available to pediatric group
2. Safety profile of propofol infusion therapy at sub-anesthetic dosing confirmed

**14. Biostatistics:** Statistical analysis will be performed by the statistician within the Department of Anesthesiology & Pain Management at UT Southwestern Medical Center.

---

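### Pre-specification of the efficacy tests is not documented, so the SAP's two-tailed 0.05 is only a nominal per-test level

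*SAP*

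**What the plan says.** The SAP's INTRODUCTION looks forward: the document is to set out the "statistical methods that will be used to analyze and report results". Its header reads "Document date: December 29,2023".

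Its STATISTICAL ANALYSIS section looks back. The paired t-tests on mean pain score and on mean percent change, the software and the significance level are all in the past tense: "Statistical analyses were carried out using SAS software, version 9.4". Under Sample Size Considerations the only content is "Forty patients were screened, and 38 patients participated in the study". The paragraphs on missing data, deviations and safety are mostly in the future tense.

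The protocol copy carries the line "Protocol version dated 06Jan2017". Its section 14, Biostatistics, says only who will do the work: "Statistical analysis will be performed by the statistician within the Department of Anesthesiology & Pain Management". The protocol's Primary outcome is complete resolution of headache or a 50% improvement from baseline on the 0-10 scale, and the SAP repeats this as its Primary Objective. The only planned size is in the protocol under Secondary outcomes: "Goal of subjects to be consented include: 30 to demonstrate effect".

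**The concern.** A significance level describes the false-positive risk of a confirmatory claim only if the test behind the claim was fixed before the results could influence it. Here the earliest document that names any test is one that already reports completed enrolment and completed analyses.

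The design offers no other safeguard. All subjects receive propofol, there is no comparator arm, and the pain score is one of the triggers for ending the infusion. Treating staff therefore knew the outcomes as they accrued.

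At stake is how the results are read. P-values published under the title of a statistical analysis plan will be taken as pre-specified evidence of efficacy. The outcome that the protocol did state in advance of the SAP could go unreported, because the SAP describes no analysis of it.

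**Working it through.** **Step 1. What each document fixes.** The entries come from the protocol's Primary outcome, Secondary outcomes, B. Protocol, 4. Follow-up and 14. Biostatistics, and from the SAP's STUDY OBJECTIVES and STATISTICAL ANALYSIS.

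| Element | Protocol (6 Jan 2017) | SAP (29 Dec 2023) |
|---|---|---|
| Efficacy outcome | Resolution or 50% improvement from baseline | Same in the objective; mean score and mean percent change in the tests |
| Assessment schedule | Every 10 minutes in the infusion and up to 1 hour after; calls at 24 and 48 hours | 10-60 minutes, 24 and 48 hours |
| Primary time | None | None |
| Null value or target rate | None | None |
| Test | None | Dependent samples t-test |
| Alpha | None | 0.05, two-tailed |
| Size | Goal of 30 consented | 40 screened, 38 participated; no planned size |

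The scale, the baseline reference, the 50% threshold and the visit schedule are in the protocol. The test and the alpha first appear in the SAP. The primary time and the null value appear in neither.

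**Step 2. The stated alpha.** For one test fixed in advance, the chance of a false positive is 1 - (1 - 0.05)^1 = 0.05, which reproduces the SAP's figure. The condition is a single contrast fixed in advance. The SAP names no contrast as primary, and neither document shows when any contrast was fixed. The 0.05 is thus correct as a per-test level, and the documents support no more than that.

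**Step 3. Do the t-tests analyse the stated outcome?** They do not. Take 38 children for illustration:

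- Every child improves by 50%: mean change = 50%, responders = 38/38 = 100%.
- Nineteen improve by 100% and nineteen by 0%: mean change = (19 × 100 + 19 × 0)/38 = 50%, responders = 19/38 = 50%.
- Every child improves by between 20% and 40%: the mean lies between 20% and 40%, well away from zero, but responders = 0/38 = 0%.

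The same mean can go with quite different response rates. If the t-test null is zero change (my assumption, since the SAP states none), the tests can reject even when no child meets the protocol's outcome. The SAP section headed Study Endpoints does not fill the gap: it lists the rules for ending the infusion and gives no analysis of response.

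**Step 4. Dates.** From 6 January 2017 to 29 December 2023 is just under seven years. Neither document gives the date of first enrolment, last enrolment, data access or analysis. The SAP's own text shows that it was completed after enrolment and after at least the efficacy tests. It does not show when those tests were chosen.

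**Step 5. Size.** 38 - 30 = 8 more than the goal. The two counts are not like for like: 30 is a goal for consent and 38 is the number who participated. The SAP gives no number consented, does not say that 38 were analysed at each time, and does not mention the 30.

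**The case against.** The strongest reply is that a late date and the past tense are weak evidence. The SAP mixes tenses and carries a stray numbered heading, so it may have been assembled from several sources, one of which could be an earlier plan. Its time grid follows the protocol's assessment schedule, so it does not look invented around a result. The protocol also did set a hypothesis and a baseline-referenced threshold, so it is wrong to say that nothing was specified.

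Most of this stands, and it limits the point. A reader might infer that the t-tests were chosen after the results were seen. The documents do not support that: they show an absence of documentation, not a data-driven choice. A reader might also infer that 0.05 is meaningless, or that a particular larger error rate should replace it. That does not follow either. The level is valid test by test, and the effect of testing at several times is a separate multiplicity question, to be assessed on its own terms.

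The reply does not dispose of two facts. No earlier plan is cited, and the tests listed are not the outcome that both documents name as primary.

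**Conclusion.** The point holds in this limited form: pre-specification of the efficacy tests is undocumented, and the stated primary outcome has no described analysis. The t-test p-values are nominal and should not carry a claim of demonstrated efficacy.

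The size is one of status and cannot be put as a number. The documents contain nothing from which to compute an error rate due to late choice, because the timing of that choice is unknown.

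The excess over 30 might tempt a reader to infer that enrolment was extended after a look at the data. No interim look, stopping rule or extension rule appears in either document, and 30 is worded as a goal, not a cap. Only the missing explanation is a fair criticism.

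The conclusion assumes that the two documents are the full record. An earlier dated SAP naming these tests would settle the timing question. It would not settle the missing responder analysis.

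**What to change.** 1. In the SAP's INTRODUCTION, state when the SAP was written relative to enrolment, access to the data and the running of the analyses. Cite any earlier dated version.

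2. In STATISTICAL ANALYSIS, make the protocol's outcome the main efficacy result: the proportion with complete resolution or at least a 50% reduction from baseline, with an exact 95% confidence interval. State the assessment time and when it was chosen, since the protocol gives none. Unless an earlier dated plan is cited, label the t-tests exploratory, report them as estimates with 95% confidence intervals, call any p-values nominal, and base no claim of demonstrated efficacy on them.

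3. Under Sample Size Considerations, set the protocol's goal of 30 consented beside the 38 who participated, and give the reason for the difference.

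The cost is changed wording in the SAP and report and one simple proportion from pain scores that the protocol already calls for. No new patients or data are needed. The downside is that, without an earlier plan to cite, the t-test results can no longer be presented as confirmatory.

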If propofol infusion is not successful in resolving headache, then the subjects will proceed with DHE infusion per standard of care. If the subject still has no relief, the study investigators will discuss further options with the subject and parents, including hospital admission for further therapy for outpatient subjects.

For all subjects who receive propofol infusion, follow-up will occur at 24 and 48 hours via phone call to evaluate headache status and recover information on headache symptoms and side effects.

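### With no imputation and a separate paired t-test at each time, early-responding outpatients can drop out of the latest in-unit comparisons, and the SAP gives no missing-data assumption or sensitivity analysis

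*SAP*

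**What the plan says.** **Analysis.** The SAP, Statistical Analysis, states that the "mean level of headache pain score at baseline and post-treatment (10-60 minute periods and 24- and 48-hour follow-up) was compared" by paired t-test, and that mean percent change is tested the same way. Handling of Missing Data adds "Missing data will not be imputed unless otherwise specified elsewhere in this SAP". No other section specifies anything. A Safety Analysis Set is named, but no efficacy set. The SAP does not say whether the 10 to 60 minutes run from the start or the end of the infusion.

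**Observation in the unit.** The infusion stops on response (SAP, Study Endpoints). The protocol's Concise Summary then says "subjects will be monitored for at least 30 minutes after termination of infusion", after which outpatients go home. The SAP's Study Overview repeats this in the past tense. Two other protocol sections differ. Methods, B. Protocol schedules pain scores every 10 minutes during the infusion and for up to an hour after it, whatever the response. Study termination keeps responding outpatients in the unit for one hour.

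**Phone calls.** For all infused children, "follow-up will occur at 24 and 48 hours via phone call to evaluate headache status". The protocol's follow-up section asks for a current pain score at each call.

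**The concern.** A paired t-test needs both scores, so without imputation each comparison silently becomes an available-case analysis. That does little harm when scores are missing at random with respect to pain. Here the missingness can be a consequence of doing well: response stops the infusion, the stop starts the observation period, and the end of that period sends an outpatient home. The children lost from the latest readings would then be those who responded fastest, and the late means would look worse than the truth. Means at successive times would also refer to different groups of children, so a late rise in mean pain could reflect discharge and not waning relief.

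**Working it through.** **1. Figures available.** There is no plan figure to reproduce. The documents give the number treated ("Forty patients were screened, and 38 patients participated in the study") and a bare target ("Goal of subjects to be consented include: 30 to demonstrate effect"). They give no number scored per time, response rate, standard deviation or outpatient share.

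**2. Number of times.** Six in-unit readings if scored every 10 minutes, plus 24 and 48 hours: 8 in all.

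**3. Which in-unit scores can be missing by rule.** The infusion lasts at most 10 + 10 + 40 = 60 minutes. For a responding outpatient, the last possible score is at stop time + observation period (clock from infusion start) or at the observation period itself (clock from infusion end).

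| Clock | Observation | Stop at 10 min | Stop at 20 min | Stop at 30 min or later |
|---|---|---|---|---|
| From start | 30 min | 50, 60 lost | 60 lost | none |
| From start | 1 h | none | none | none |
| From end | 30 min | 40, 50, 60 lost | 40, 50, 60 lost | 40, 50, 60 lost |
| From end | 1 h | none | none | none |

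So at most 2 of 8 times (start clock) or 3 of 8 (end clock) are exposed, and only for outpatients. Because 30 minutes is a minimum, these are scores that can be lost, not scores that must be.

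**4. Size at 60 minutes.** Assumptions: 60% respond, with response times spread evenly over the six readings; responders average 2.5 and others 7.0; outpatient responders leave at exactly 30 minutes.
- Mean in all children: 0.4 × 7.0 + 0.6 × 2.5 = 4.30.
- Start clock, all outpatients: share lost 0.60 × 2/6 = 0.20; observed mean (0.4 × 7.0 + 0.4 × 2.5)/0.8 = 4.75; gap 0.45.
- Start clock, half outpatients: share lost 0.10; observed mean (0.4 × 7.0 + 0.5 × 2.5)/0.9 = 4.50; gap 0.20.
- End clock, half outpatients: share lost 0.30; observed mean (0.4 × 7.0 + 0.3 × 2.5)/0.7 = 5.07; gap 0.77.

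In general, gap = p × (b − a), where p is the share lost, a their mean change and b the mean change in the rest. With a = −5, b = −2.5 and p = 10%, 20% or 30%, the gap is 0.25, 0.50 or 0.75. With b = −1 it is 0.40, 0.80 or 1.20.

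**5. What a mixed model does.** Simulated under the 30-minute text, mean change at 60 minutes from infusion start:

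| | True | Complete-case | Mixed model |
|---|---|---|---|
| All outpatients | −3.75 | −3.29 | −3.93 to −4.00 |
| Half outpatients | −3.71 | −3.51 | about −3.79 |

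The complete-case error is 0.46 or 0.20 in the unfavourable direction. The model's error is 0.18 to 0.25, or about 0.08, in the favourable direction. Spread and correlation had to be assumed, so only the direction and rough size should be relied on.

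**6. Phone calls.** If 10% to 30% are not reached and differ by 2 points from the rest, the mean shifts by 0.1 × 2 = 0.2 to 0.3 × 2 = 0.6, in either direction.

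**The case against.** Four stronger readings are tempting, and the documents do not support them.

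- *Every time point rests on an outcome-selected subset.* The earliest readings (10 to 30 minutes) are complete by rule on either clock. Under the one-hour text all in-unit readings are.
- *The phone-call rule selects on outcome.* It covers every infused child and asks each for a score. Nothing shows that unreached children would be the relapsed ones. The SAP also plans no 24-hour relief rate that non-contact could inflate.
- *Over-sedated children go unscored.* No passage stops scoring for them.
- *The primary outcome is compromised.* Response is essentially the criterion that stops the infusion, so responder status is known before any discharge.

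The sponsor can add two fair points. The in-unit error is conservative, and in an uncontrolled study a model that errs favourably is not an obvious improvement. And a mixed model imputes nothing, so the missing-data sentence could stand unchanged beside it.

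Both points hold. They argue for keeping the t-tests next to the model and for locating the fault in the separate complete-case tests, not in the refusal to impute. They do not supply the missing assumption or sensitivity analysis. Nor does the one-hour text settle the matter, because the SAP itself reports the 30-minute minimum as what was done.

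**Conclusion.** The point holds for the late in-unit readings, and conditionally. On the SAP's own account of discharge, a score can be absent because the child responded, and the planned tests have no means of allowing for it. The gaps of about 0.2 and 0.5 points at 60 minutes from infusion start rest on the assumed response rate, response times and pain levels and on discharge at exactly 30 minutes. A smaller outpatient share shrinks the gap; earlier response or an infusion-end clock enlarges it. If children were in fact scored for a full hour after the infusion, the in-unit gap by rule is nil.

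At 24 and 48 hours the weakness is narrower: the SAP does not say how an unreached child is counted. A separate matter, which no missing-data method would cure, is that non-responders' later scores follow DHE.

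**What to change.** 1. Reconcile the 30-minute and one-hour passages, state which applied to the collected data, and define the clock for the 10 to 60 minute readings.
2. Analyse change from baseline in one repeated-measures mixed model on all available scores, with time as a factor and within-child correlation. Report the estimate, 95% confidence interval and number observed at each time. Early discharge follows from scores already recorded, and such a model can use that information where separate t-tests cannot.
3. Keep the planned paired t-tests as a sensitivity analysis. The two sets of results can err in opposite directions, so both should be shown.
4. At 24 and 48 hours, keep every infused child in the denominator and give bounds that assign unreached children first the most and then the least favourable outcome. The missing-data sentence allows exceptions specified in the SAP, so write this one in.

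The cost is SAP wording and a modest amount of extra analysis in the SAS software already named; no new data are needed. The 24- and 48-hour results may look less favourable, and the bounds add a summary that is not now planned.
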